2.3.1 Full analysis set

The Full Analysis Set (FAS) includes all patients who received at least one dose of PDR001. Patients will be analyzed according to the planned treatment (dose level and regimen). The FAS will be used for all listings of raw data. Unless otherwise specified, the FAS will be the default analysis set used for all analyses.

2.3.2 Safety set

The Safety Set (SS) includes all patients from the FAS who have received at least one dose of PDR001 and had at least one valid post-baseline safety assessment. The statement that a patient had no AEs (on the AE eCRF) constitutes a valid safety assessment. Patients will be classified according to treatment received, where treatment received is defined as:

- The treatment assigned if it was received at least once, or
- The first treatment received when starting therapy with study treatment if the assigned treatment was never received.

The safety set will be used for the safety summary of the study.

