## **Amendment 06 (27-Jul-2017)**

### **Amendment rationale**

The main purpose of this amendment is to remove the requirement for progression on prior therapy for patients with anaplastic thyroid cancer; patients are no longer required to have received therapy prior to being eligible for treatment with PDR001. Outcomes for patients with this disease are dismal with a median life expectancy after diagnosis of less than six months

(Neff et al 2008). Given the poor outcome after standard therapy current NCCN treatment guidelines recommend that all patients be considered for clinical trials (Neff et al. 2008; NCCN Guidelines (version 2.2017): Thyroid Carcinoma).

Some data suggest that this disease may be sensitive to PD-1 blockade. In published data, six of eight tumors from patients with anaplastic thyroid cancer expressed high levels of PD-L1 on tumor cells and were infiltrated by lymphocytes (Bastman et al, 2016). In preliminary data from the first 12 anaplastic thyroid cancer patients treated and evaluable for efficacy in the phase II part of this ongoing study (CPDR001X2101), one patient has a confirmed partial response (~ -52% by RECIST criteria) and an additional patient has a confirmed reduction in their disease burden (~ -14% by RECIST criteria). However, because of the aggressive nature of the disease, most anaplastic thyroid cancer patients on the trial to date have developed progressive disease or died prior to the first scheduled imaging evaluation (at eight weeks), allowing little time for immunotherapy to provide benefit. The inclusion criteria are therefore revised in this amendment to allow treatment earlier in the disease course.

Specific changes to inclusion criterion #4 for patients with anaplastic thyroid cancer include:

1. Patients are not required to have received or progressed on a prior therapy.
2. Patients must not be at short term risk for life threatening complications (such as airway compromise or bleeding from locoregional or metastatic disease).
3. Chemoradiation and/or surgery should be considered prior to study entry for those patients with locally advanced disease if those therapies are considered to be in the best interest of the patient.

Other changes to this protocol include:

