### 10.1.2 Safety Set

The Safety Set includes all patients from the FAS who have received at least one dose of PDR001 and had at least one valid post-baseline safety assessment. The statement that a patient had no AEs (on the AE eCRF) constitutes a valid safety assessment. Patients will be classified according to treatment received, where treatment received is defined as:

1. The treatment assigned if it was received at least once, or
2. The first treatment received when starting therapy with study treatment if the assigned treatment was never received.

The safety set will be used for the safety summary of the study.

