2.3.8 Analysis set exclusion

Patients will be excluded from the analysis sets based on the protocol deviations and specific non-protocol deviations entered in the database. All protocol deviations and non-protocol deviations leading to exclusion from specific analysis sets will be identified before database lock. Protocol and non-protocol deviations leading to exclusion from specific analysis sets and reasons for exclusion from populations will be tabulated/listed by treatment (Phase I) /indication and treatment (Phase II).

Table 2-1 displays non-protocol deviations leading to exclusion from analysis set definitions and Table 2-2 displays protocol deviations leading to exclusion from analysis set definitions.

Table 2-1 Non-protocol deviation leading to exclusion from analysis set definitions

Summary of non PD	Analysis set(s) to be excluded
No valid post-baseline safety assessment	SS
No administration of study treatment	FAS, SS, PPS, DDS, DDP, PAS,
	Immunogenicity prevalence set, Immunogenicity incidence set
 Patient, who has not experienced DLT, was not observed for ≥ 28 days following the C1D1 or had not completed the required safety evaluations for Cycle 1 or 	DDS
 Patient who has not experienced DLT, received <70% planned doses at each time of dosing in Cycle 1. 	
The patient did not receive at least one dose of PDR001 during cycle 1 or did not have sufficient PK data in cycle 3 to evaluate the AUC _(0-336h) .	DDP
Patient did not have at least one measurable PDR001 concentration in cycle 1	PAS
No determinant IG sample at both baseline and post-baseline	Immunogenicity prevalence set
No determinant IG sample at baseline or post- baseline or both	Immunogenicity incidence set

Table 2-2 Protocol deviation leading to exclusion from analysis set definitions

Protocol Deviation ID (DVSPID)	Summary of PD	Analysis set(s) to be excluded
INCL01	Written informed consent must be obtained prior to screen procedures.	FAS, SS, PPS, DDS, DDP, PAS, Immunogenicity prevalence set, Immunogenicity incidence set

Novartis	Confidential	Page 22
SAP final CSR	24-Jul-2020 (11:48)	CPDR001X2101

	,	,
Protocol Deviation ID (DVSPID)	Summary of PD	Analysis set(s) to be excluded
INCL04	In the Phase II part, patient does not have at least one tumor lesion meeting measurable disease criteria as determined by RECIST v1.1.	PPS
INCL05	In the Phase II part, patient was not a patient with either NSCLC, melanoma, TNBC, or ATC.	PPS

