3.5 Safety evaluation

All safety analyses will be based on the Safety Set. The only exceptions will be the summaries of dose limiting toxicities (DLTs) for which the DDS will be used and presented by treatment.

The overall observation period is divided into three mutually exclusive segments:

- 1. pre-treatment period: from day of patient's informed consent to the day before first dose of study treatment
- 2. on-treatment period: from day of first dose of study treatment to 30 days after last dose of study treatment
- 3. post-treatment period: starting at day 31 after last dose of study treatment.

SAP final CSR

Safety summaries will primarily be based on all data from the on-treatment period. Following last administration of PDR001, adverse events (including serious adverse events), and new antineoplastic therapies are collected for a period of 150 days. Following start of new antineoplastic therapy, only study treatment related adverse events will be collected. Select summaries of related adverse events will be produced for the combined on-treatment and posttreatment periods ([CPDR001X2101 Amendment 8 Section 10.5.3.2]).

3.5.1 **Dose-limiting toxicities**

In the Phase I dose-escalation part, DLTs are listed by primary system organ class, worst grade based on the CTCAE version 4.03, and by dose cohort. The Dose determining safety set is used for this summary. By-patient listings will be provided.

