- Overview of adverse events and deaths (number and % of subjects who died, with any AE, any SAE, any dose reductions/interruptions, AE leading to discontinuation)
- AEs by SOC and PT, summarized by relationship (all AEs and AEs related to study treatment);
- Seriousness (SAEs, and non-SAEs);
- Leading to treatment discontinuation;
- Leading to dose interruption/adjustment;
- Requiring additional therapy;
- Leading to fatal outcome;
- Dose limiting toxicities by PT

The following summaries will be produced for all AEs starting or worsening during the ontreatment or post-treatment periods:

- AEs related to study treatment by SOC and PT;
- SAEs related to study treatment

The following listings will be produced:

- All adverse events (safety set)
- Adverse events among subjects who were not treated (all screened subjects)

Deaths (CSR Outputs)

Separate summaries for on-treatment and all deaths (including post-treatment death) will be produced by system organ class and preferred term.

All deaths will be listed for the safety set, deaths occurring after the on-treatment period will be flagged. A separate listing of deaths prior to starting treatment will be provided for all screened subjects.

EudraCT and clinicaltrials.gov requirements for AEs and Deaths summaries

For the legal requirements of clinicaltrials.gov and EudraCT, two required tables on treatmentemergent adverse events which are not serious adverse events with an incidence greater than 5% and on treatment emergent SAEs and SAEs suspected to be related to study treatment will be provided by SOC and PT on the safety set population in the final CSR.

If for a same patient, several consecutive AEs (irrespective of study treatment causality, seriousness and severity) occurred with the same SOC and PT:

- a single occurrence will be counted if there is ≤ 1 day gap between the end date of the preceding AE and the start date of the consecutive AE
- more than one occurrence will be counted if there is > 1 day gap between the end date of the preceding AE and the start date of the consecutive AE

For occurrence, the presence of at least one SAE / SAE suspected to be related to study treatment / non SAE has to be checked in a block e.g., among AE's in a ≤ 1 day gap block, if at least one SAE is occurring, then one occurrence is calculated for that SAE.

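### The Safety Set can drop a treated patient who dies before any safety assessment is recorded; the gap is narrow and cheap to close

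*SAP*

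**What the plan says.** SAP 2.3.1 makes the FAS everyone who was dosed: "The Full Analysis Set (FAS) includes all patients who received at least one dose of PDR001". SAP 2.3.2 starts from the FAS and adds that the patient must have "had at least one valid post-baseline safety assessment". Because the FAS already consists of dosed patients, this added condition is the only part of the definition that can make the two sets differ in membership. Protocol 10.1.2 has the same definition: it opens with "The Safety Set includes all patients from the FAS who have received at least one dose of PDR001" and attaches the same condition.

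SAP Table 2-1 (section 2.3.8) turns the condition into an exclusion. Its first row, "No valid post-baseline safety assessment", removes the patient from the Safety Set alone. A separate row deals with patients who were never dosed.

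Both documents soften the rule: "The statement that a patient had no AEs (on the AE eCRF) constitutes a valid safety assessment". Neither says whether an entry on the Death form, or an AE record by itself, also counts.

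On use of the set, SAP 3.5 says "All safety analyses will be based on the Safety Set", with DLT summaries on the DDS as the one exception. SAP 3.2.1 uses it for exposure as well. On deaths, SAP 3.5.2.2 says "All deaths will be listed for the safety set, deaths occurring after the on-treatment period will be flagged". The only other death listing planned covers deaths before treatment started. Protocol 10.5.3.2 commits to summarizing every on-treatment and post-treatment death.

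**The concern.** The condition can depend on outcome. A dosed patient is most likely to lack any post-dose assessment because of death, rapid deterioration or loss to follow-up soon after the first infusion. A safety population should not lose patients for that reason.

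A treated patient outside the Safety Set also falls between the two death listings: not in the set, yet dosed. The commitment in Protocol 10.5.3.2 would then not be met for that patient. The same patient stays in the FAS, and Protocol 10.4.3 counts a best response of unknown or not assessed as a failure for ORR. Efficacy and safety could therefore rest on slightly different treated populations.

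The setting makes early death plausible. The Amendment 06 rationale reports that "most anaplastic thyroid cancer patients on the trial to date have developed progressive disease or died prior to the first scheduled imaging evaluation".

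**Working it through.** No stated figure depends on this point, so there is none to reproduce. The check is a trace of the definitions followed by an illustration.

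**Who is dropped.** All of the following must hold: at least one dose was given; no AE is recorded; there is no entry stating that no AEs occurred; and no other post-dose safety assessment exists.

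**How long the window is.** Protocol 7.2.2.2 and 7.2.2.5 put vital signs and safety laboratory samples before the infusion on dosing days, so Day 1 values are baseline. Protocol 7.2.2.1 brings the next physical examination on Cycle 1 Day 8. Protocol 7.2.2 collects AEs at every visit, and Tables 7-6 and 7-7 both bring patients in for PK on Day 2. A PK sample is not itself a safety assessment, but the visit is an occasion to record AEs. The window is therefore hours to about a week.

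**Whether a death can leave no AE record.**
- SAP 3.5.2.1 does not use CTCAE grade 5 and puts death information on separate Death pages.
- Protocol 8.2.1 makes a fatal event an SAE, and 8.2.2 requires every SAE to be reported whatever its cause. The default is therefore a fatal SAE record.
- Protocol 8.1.1 exempts fatal progression only when it has been documented by a suitable method such as RECIST or irRC. The first scheduled post-dose scan is at 8 weeks (Protocol 7.2.1), so a death in the first days would ordinarily lack that documentation.
- What remains is mainly progression judged on clinical grounds, which Protocol 8.2.1 says should be rare, or a form left incomplete.

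**Size if anyone is dropped.** Treated counts are in the Amendment 08 study status: 118 + 61 + 40 + 42 = 261 in Phase II, and 58 + 261 = 319 in all. Let n be the number treated, k the early deaths dropped and d the other deaths counted. Both k and d are assumptions; the documents give neither.

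- Death rate as planned: d/(n − k)
- Death rate in all treated: (d + k)/n

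Anaplastic thyroid cancer group, n = 42, d = 4:

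| k | As planned | All treated | Understatement (points) |
|---|---|---|---|
| 1 | 4/41 = 9.8% | 5/42 = 11.9% | 2.1 |
| 2 | 4/40 = 10.0% | 6/42 = 14.3% | 4.3 |
| 3 | 4/39 = 10.3% | 7/42 = 16.7% | 6.4 |

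With d = 0 the understatement is 2.4, 4.8 and 7.1 points. With d = 8 it is 1.9, 3.8 and 5.7 points.

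Across all 319 patients with d = 10: 10/318 = 3.14% against 11/319 = 3.45% for k = 1, and 10/316 = 3.16% against 13/319 = 4.08% for k = 3. The understatement is 0.3 to 0.9 points.

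AE percentages move the other way, because dropped patients have no recorded AE and leave only the denominator. With 20 of 42 patients having a given AE (assumed), the true 47.6% is shown as 20/41 = 48.8%, 20/40 = 50.0% or 20/39 = 51.3% for k = 1, 2, 3. That is an overstatement of 1.2 to 3.7 points.

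**The case against.** The strongest reply is that other rules close most of the gap. An entry stating that there were no AEs keeps the patient in, AEs are sought from the first visits onward, and an early death should arrive as a fatal SAE. All of this stands, and it is why the number affected may be zero. It does not close the gap entirely: no rule says that a Death-form entry counts as an assessment, and inclusion can turn on whether a form was completed.

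Four stronger readings are tempting, and the documents do not support them.

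- **Early deaths would vanish from the report.** They would not. Disposition is on the FAS with death among the reasons for ending treatment (SAP 3.1.1 and 2.1.2). PFS is on the FAS and counts death from any cause (SAP 3.4). SAP 2.3.8 tabulates or lists the reasons for exclusion from analysis sets. What is at risk is the safety tables and the death listing.
- **The Amendment 06 statement shows that many patients are affected.** It concerns progression or death before the 8-week scan, not before the first safety assessment. It also describes patients enrolled before that amendment excluded those at short-term risk of life-threatening complications.
- **Every bias runs in one direction.** Death rates would be understated, but AE percentages would be slightly overstated.
- **The SAP departs from the protocol.** Their definitions agree. This is a weakness in a shared definition. The nearest thing to a conflict is the general rule in SAP 2.3.1 that raw-data listings use the FAS, set against the specific rule that the death listing uses the Safety Set.

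**Conclusion.** The point holds in a limited form, as a low-cost improvement. The text allows a treated patient to be left out of the AE and death tables, the death listing and their denominators for a reason that can depend on outcome. The route is narrow, and neither document says whether anyone took it. The percentages rest on assumed counts: one to three dropped deaths, with none to eight others in the group of 42. Over that range the understatement of the death rate is 1.9 to 7.1 points. If no treated patient lacks an assessment, no result changes.

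**What to change.** Define the Safety Set in SAP 2.3.2 and Protocol 10.1.2 as all patients given at least one dose of PDR001, and delete the first row of Table 2-1. The rule for classifying patients by treatment received stays. The set would then contain the same patients as the FAS (319 treated, 42 in the anaplastic thyroid cancer group). The Safety Set death tables and listing would then cover all treated patients, as Protocol 10.5.3.2 promises.

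Leave the DDS criteria in SAP 2.3.4 unchanged. They already require either a DLT, or 70% of planned dosing together with at least 28 days of observation and enough safety data. A patient newly admitted to the Safety Set would not enter the DDS by this change.

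If the definition cannot be reopened, a weaker alternative is to state in the SAP that a death or AE record counts as a valid post-baseline assessment, and to report any treated patient still outside the set.

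The cost is a short wording change in both documents; SAP section 1 provides for an amendment before database lock or an addendum after it. The denominator may grow, which would lower AE percentages slightly. The set may also differ a little from the one used in an earlier primary CSR, in which case the final CSR should say so and give the count.

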2.3.3 Per-Protocol set

The Per Protocol Set (PPS) consists of a subset of FAS patients in the Phase II part who meet the following criteria:

Presence of at least one measurable lesion at baseline according to RECIST v1.1 as per Appendix 1 in [CPDR001X2101 Amendment 8]

- At least 2 post-baseline tumor assessments (unless disease progression is observed before that time)
- Have not been previously treated with PD-1- or PD-L1-directed therapy

Patients will be classified according to treatment received.

The PPS will be used in the Phase II part of the study only and will define the patients used in the sensitivity analysis of the primary endpoint [CPDR001X2101 Amendment 8 Section 10.4.4]. If the PPS and the FAS are identical, then analyses described by the PPS in study protocol will not be performed.

2.3.4 Dose-determining safety set

The dose-determining safety set (DDS) consists of all patients from the safety set in Phase I dose escalation who either meet the following minimum exposure criterion and have sufficient safety evaluations, or have experienced a DLT during Cycle 1. A patient is considered to have met the minimum exposure criterion if he/she receives at least 70% of the planned dose of PDR001 at each time of dosing during Cycle 1.

Patients who do not experience DLT during Cycle 1 are considered to have sufficient safety evaluations if they have been observed for ≥ 28 days following the first dose, and are considered by both the Sponsor and Investigators to have enough safety data to conclude that a DLT did not occur.

Patients who do not meet these minimum safety evaluation requirements will be regarded as ineligible for the DDS and an additional patient may be recruited (see [CPDR001X2101 Amendment 8 Section 7.1.4.1]).

2.3.5 Dose-determining pharmacokinetic analysis set

The dose-determining pharmacokinetic set (DDP) consists of all patients in the Phase I dose escalation part who have received at least one dose of PDR001 during Cycle 1 and have sufficient PK data in cycle 3 to evaluate the AUC_{(0-336h).} DDP will only be used for analysis of study treatment exposure.

2.3.6 Pharmacokinetic analysis set

The pharmacokinetic analysis set (PAS) consists of all patients who have at least one blood sample providing evaluable PK data. The PAS will be used for summaries of PK concentration data, and PK parameters, except that DDP will be used in the dose-exposure analysis in the Phase I dose-escalation part.

Note: Patients may be removed from the estimation of certain PK parameters on an individual basis depending on the number of available blood samples. These patients will be identified at the time of analysis. Any concentration data and PK parameter data resulting from non-evaluable profile will only be listed in data listings but will not be included in summary tables and figures.

2.3.7 Immunogenicity (IG) analysis sets

The Immunogenicity prevalence set includes all subjects in the Full analysis set with a determinant baseline IG sample **or** at least one determinant post-baseline IG sample.

The Immunogenicity incidence set includes all subjects in the Immunogenicity prevalence set with a determinant baseline IG sample and at least one determinant post-baseline IG sample.

See Section 3.8.1 for the definition of determinant.

2.3.8 Analysis set exclusion

Patients will be excluded from the analysis sets based on the protocol deviations and specific non-protocol deviations entered in the database. All protocol deviations and non-protocol deviations leading to exclusion from specific analysis sets will be identified before database lock. Protocol and non-protocol deviations leading to exclusion from specific analysis sets and reasons for exclusion from populations will be tabulated/listed by treatment (Phase I) /indication and treatment (Phase II).

Table 2-1 displays non-protocol deviations leading to exclusion from analysis set definitions and Table 2-2 displays protocol deviations leading to exclusion from analysis set definitions.

Table 2-1 Non-protocol deviation leading to exclusion from analysis set definitions

Summary of non PD	Analysis set(s) to be excluded
No valid post-baseline safety assessment	SS
No administration of study treatment	FAS, SS, PPS, DDS, DDP, PAS,
	Immunogenicity prevalence set, Immunogenicity incidence set
 Patient, who has not experienced DLT, was not observed for ≥ 28 days following the C1D1 or had not completed the required safety evaluations for Cycle 1 or 	DDS
 Patient who has not experienced DLT, received <70% planned doses at each time of dosing in Cycle 1. 	
The patient did not receive at least one dose of PDR001 during cycle 1 or did not have sufficient PK data in cycle 3 to evaluate the AUC _(0-336h) .	DDP
Patient did not have at least one measurable PDR001 concentration in cycle 1	PAS
No determinant IG sample at both baseline and post-baseline	Immunogenicity prevalence set
No determinant IG sample at baseline or post- baseline or both	Immunogenicity incidence set

Table 2-2 Protocol deviation leading to exclusion from analysis set definitions

Protocol Deviation ID (DVSPID)	Summary of PD	Analysis set(s) to be excluded
INCL01	Written informed consent must be obtained prior to screen procedures.	FAS, SS, PPS, DDS, DDP, PAS, Immunogenicity prevalence set, Immunogenicity incidence set

Novartis	Confidential	Page 22
SAP final CSR	24-Jul-2020 (11:48)	CPDR001X2101

	,	,
Protocol Deviation ID (DVSPID)	Summary of PD	Analysis set(s) to be excluded
INCL04	In the Phase II part, patient does not have at least one tumor lesion meeting measurable disease criteria as determined by RECIST v1.1.	PPS
INCL05	In the Phase II part, patient was not a patient with either NSCLC, melanoma, TNBC, or ATC.	PPS

